### **4.3.3 Investigational Medicinal Product Accountability**

All IMPs required for completion of this study (obinutuzumab, *rituximab*, and idasanutlin) will be provided by the Sponsor. The study site will acknowledge receipt of IMPs using the IxRS to confirm the shipment condition and content. Any damaged shipments will be replaced.

IMPs will either be disposed of at the study site according to the study site's institutional standard operating procedure or returned to the Sponsor with the appropriate documentation. The site's method of IMP destruction must be agreed to by the Sponsor. The site must obtain written authorization from the Sponsor before any IMP is destroyed, and IMP destruction must be documented on the appropriate form.

Accurate records of all IMPs received at, dispensed from, returned to, and disposed of by the study site should be recorded on the Drug Inventory Log.

### **4.3.4 Post-Study Access to Obinutuzumab, Rituximab, and Idasanutlin**

Currently, the Sponsor does not have any plans to provide obinutuzumab, *rituximab*, or idasanutlin or any other study treatments or interventions to patients who have completed the study. The Sponsor will evaluate whether to continue providing obinutuzumab, *rituximab*, and idasanutlin in accordance with the Roche Global Policy on Continued Access to Investigational Medicinal Product, available at the following Website:

[http://www.roche.com/policy\\_continued\\_access\\_to\\_investigational\\_medicines.pdf](http://www.roche.com/policy_continued_access_to_investigational_medicines.pdf)

## **4.4 CONCOMITANT THERAPY**

Concomitant therapy includes any medication (e.g., prescription drugs, over-the-counter drugs, herbal or homeopathic remedies, nutritional supplements) used by a patient from 14 days prior to the screening period to the visit at EO1 or at the end of Maintenance *or consolidation* treatment, whichever occurs later. All such medications should be reported to the investigator and recorded on the Concomitant Medications eCRF.

### **4.4.1 Permitted Therapy**

Premedication is permitted as described in Section 4.3.2.6.

Patients who use oral contraceptives, hormone-replacement therapy, or other maintenance therapy should continue their use.

During the dose-escalation phase, granulocyte colony-stimulating factor (G-CSF) is not permitted during the first cycle, unless the patient experiences a DLT of neutropenia.

During the expansion phase, G-CSF is permitted as clinically indicated per American Society of Clinical Oncology (ASCO), European Organization for Research and

Treatment of Cancer (EORTC), and European Society for Medical Oncology (ESMO) guidelines (Smith et al. 2006) or per each site's institutional standards.

Prophylactic treatment with antibiotics should be administered per standard of care.

Necessary supportive measures for optimal medical care will be given throughout the study according to institutional standards.

#### **4.4.2 Prohibited Therapy**

Use of the following therapies (excluding protocol-specified treatments) is prohibited during the study:

- Any anti-cancer therapy, approved or investigational, other than intrathecal central nervous system prophylaxis
- Hormonal therapy other than contraceptives, stable hormone-replacement therapy, or megestrol acetate
- Biologic agents other than hematopoietic growth factors (as described in Section 5.1.1.3)
- Use of oral or parental anticoagulants/antiplatelet agents (e.g., chronic daily treatment with aspirin [ $> 325$  mg/day], clopidogrel, warfarin, systemic low molecular weight heparin (LMWH), or subcutaneous anticoagulant prophylaxis) are prohibited during the study unless treatment can be discontinued 7 days (or 5 half-lives) prior to initiation of study treatment (except used as flushes for indwelling catheters)
- Vaccination with live vaccines is not recommended during treatment with obinutuzumab or rituximab and until B-cell recovery.

Idasanutlin is metabolized mainly by CYP3A, CYP2C8, and UGT (UDP glucuronosyltransferase) enzymes. *Due to the fact that idasanutlin PK exposure is only minimally changed during treatment with a strong CYP3A inhibitor (posaconazole), it is not a sensitive CYP3A or CYP2C8 substrate as summarized in Section 1.3.3.1 and thus its metabolism may only be affected by concomitant CYP3A and CYP2C8 inducers or dual CYP3A and CYP2C8 inhibition. Idasanutlin inhibits CYP2C8 metabolism, which may affect concomitant CYP2C8 substrates, and its M4 metabolite is an organic anion-transporting polypeptide (OATP)-1B1/3 transporter inhibitor that may affect concomitant OATP1B1/3 substrates. Thus, in order to prevent undesirable drug-drug interactions, the use of any medication listed in Table 10 (CYP2C8 substrates and inhibitors), Table 11 (strong CYP3A inducers), and Table 12 (OATP1B1/3 substrates) are either prohibited during the study within the DLT evaluation window in the escalation phase or allowed after the DLT evaluation window, after washing out in sufficient duration (for inhibitors) or concomitant use with caution (for inducers) in order to prevent undesirable drug-drug interactions. Note that gemfibrozil is also a UGT1A3 inhibitor that will be excluded from this study and that CYP3A4 inhibitors are not excluded.*

Substrates and inhibitors listed in Table 10 and Table 12 must be discontinued 7 days prior to start of study treatment. Inducers listed in Table 11 must be discontinued 14 days prior to start of study treatment.

**Table 10 Prohibited CYP2C8 Substrates, Inhibitors, and Inducers**

Substrates	Inhibitors a	Inducer b
amiodarone	gemfibrozil (also a UGT1A3 inhibitor)	rifampicin
amodiaquine		
cerivastatin	monteleukast	
chloroquine	pioglitazone	
ibuprofen		
lovastatin	quercetin	
montelukast		
paclitaxel		
pioglitazone	rosiglitazone	
repaglinide		
rosiglitazone	trimethoprim	
simvastatin	•	
torasemide		

a When CYP3A inhibitors are in use, concomitant use of idasanutlin with CYP2C8 inhibitors is to be avoided, to prevent idasanutlin exposure elevation with potentially increased toxicities; use an alternative medication that is not an inhibitor. If these CYP2C8 inhibitors must be used medically, they are allowed during the study only if the patient has completed the DLT evaluation window (if patient is in a dose-escalation cohort) and idasanutlin is withheld in that cycle. After discontinuation of the CYP2C8 inhibitor, wait for 7 days before restarting idasanutlin treatment.

b Concomitant use of idasanutlin with the CYP2C8 inducer rifampicin is to be avoided to prevent idasanutlin exposure loss compromising efficacy; consider alternative medications. If a patient requires use of this medication, use with caution and contact the Roche Medical Monitor (refer to Section 5.4.1) for guidance. The inducer is allowed during the study only if the patient has completed the DLT evaluation window (if patient is in a dose-escalation cohort).

**Table 11 Prohibited *Strong* CYP3A4 Inducers**

Inducers (Strong) a
carbamazepine
cyproterone
efavirenz
enzalutamine
etravirine
mitotane
modafinil
nevirapine
oxcarbazepine
phenobarbital
phenytoin
rifampicin
St. John's wort

a Concomitant use of idasanutlin with strong CYP3A inducers is to be avoided to prevent idasanutlin exposure loss compromising efficacy; consider alternative medications. If a patient requires use of these medications, use with caution and contact the Roche Medical Monitor (refer to Section 5.4.1) for guidance. The inducers are allowed during the study only if the patient has completed the DLT evaluation window (if patient is in a dose-escalation cohort).

**Table 12 Prohibited OATP1B1/3 Substrates**

OATP1B1/2 Substrates
asunaprevir
atorvastatin
atrasentan
bosentan
cerivastatin
danoprevir
docetaxel
ezetimibe
fluvastatin
fexofenadine
glyburide
irinotecan
nateglinide
olmesartan
paclitaxel
pitavastatin
pravastatin
repaglinide
rifampin
rosuvastatin
simvastatin acid
telmisartan
valsartan

The above lists of medications are not necessarily comprehensive. Thus, the investigator should consult the prescribing information for any concomitant medication as well as the internet references provided below when determining whether a certain medication should be inhibited by the above rationale. In addition, the investigator should contact the Medical Monitor if questions arise regarding medications not listed above.

<http://www.fda.gov/Drugs/DevelopmentApprovalProcess/DevelopmentResources/DrugInteractionsLabeling/ucm093664.htm>

<http://medicine.iupui.edu/clinpharm/ddis/table.aspx>

## 4.5 STUDY ASSESSMENTS

See [Appendix 1](#) and [Appendix 2](#) for the overall schedule of activities and [Appendix 3](#) for the PK schedules of assessments performed during the study.

### 4.5.1 Informed Consent Forms and Screening Log

Written informed consent for participation in the study must be obtained before performing any study-related procedures. Informed Consent Forms for enrolled patients and for patients who are not subsequently enrolled will be maintained at the study site.

All screening evaluations must be completed and reviewed to confirm that patients meet all eligibility criteria before enrollment. The investigator will maintain a screening log to record details of all patients screened and to confirm eligibility or record reasons for screening failure, as applicable.

Results of standard-of-care tests or examinations performed prior to obtaining informed consent and, within the defined window, may be used as screening and baseline assessments (see [Appendix 1](#) and [Appendix 2](#)); such tests do not need to be repeated for screening purposes (e.g., screening tumor assessment).

Study treatment should be initiated within 28 days after the Informed Consent Form has been signed. *Those patients who fail screening based on longer waiting time for certain results or due to study technical reasons (such as cohort on hold) can be rescreened once at a later date if they were deemed eligible before the screen failure. The decision to rescreen individual patients will be made jointly by the Roche Medical Monitor and the investigator and any other person the investigator or Medical Monitor considers necessary to assist with this decision. Any such decision and the reasons for it will be clearly documented. Any out of window assessments need to be repeated and undergo a complete review by the Roche Medical Monitor.*

### 4.5.2 Medical History and Demographic Data

Medical history includes clinically significant diseases, surgeries, reproductive status, smoking history, and alcohol and drug abuse. In addition, all medications (e.g., prescription drugs, over-the-counter drugs, herbal or homeopathic remedies, nutritional supplements) used by the patient within 7 days prior to the screening period will be recorded.

Demographic data will include age, sex, and self-reported race/ethnicity.

The following clinical parameters relative to disease history, diagnosis, and prognostic indices will be recorded at screening:

- Date of initial diagnosis
- ECOG Performance Status (see [Appendix 6](#))
- Ann Arbor staging (see [Appendix 7](#))

- B symptoms (unexplained fever >38°C, night sweats, and unexplained weight loss > 10% of body weight over 6 months)
- For patients with FL: Follicular Lymphoma International Prognostic Index (FLIPI) and FLIPI2 (see [Appendix 8](#))
- For patients with DLBCL: IPI (see [Appendix 8](#))
- Previous lines of anti-lymphoma treatment as well as response to prior therapy, date of disease progression in relation to start date of prior treatment, and date of last dose of prior treatment

### **4.5.3 Physical Examinations**

A complete physical examination should be performed at screening and should include an evaluation of the head, eyes, ears, nose, and throat and the cardiovascular, dermatological, musculoskeletal, respiratory, gastrointestinal, genitourinary, and neurological systems. Any abnormality identified at baseline should be recorded on the General Medical History and Baseline Conditions eCRF.

As part of tumor assessment, the physical examination should include evaluation for the presence of enlarged nodes, palpable hepatomegaly, and splenomegaly. This information will be recorded on the appropriate Tumor Assessment eCRF.

At subsequent visits (or as clinically indicated), targeted (limited, symptom-directed) physical examinations should be performed. Targeted physical examinations should be limited to systems of primary relevance (e.g., cardiovascular and respiratory systems), systems associated with symptoms (newly emergent or monitored from baseline), and areas associated with tumor assessment (lymph nodes, liver, spleen, and any other areas identified at baseline) (see Section [4.5.5](#)).

Changes from baseline abnormalities should be recorded in patient notes. New or worsened clinically significant abnormalities should be recorded as adverse events on the Adverse Event eCRF.

### **4.5.4 Vital Signs**

Vital signs will include measurements of respiratory rate, pulse rate, body temperature, and systolic and diastolic blood pressures while the patient is in a seated position. Vital sign measurements will be performed as outlined in the schedules of assessments (see [Appendix 1](#) and [Appendix 2](#)), but the associated data, other than the data collected at screening, do not need to be recorded on the eCRF (except in the case of an adverse event).

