### **Safety Objectives**

The safety objectives for this study are as follows:

- To determine the recommended Phase II dose (RP2D) for idasanutlin when given in combination with a fixed dose of obinutuzumab *or rituximab* on the basis of the incidence of DLTs during the *DLT windows* of study treatment
- To evaluate the safety and tolerability of obinutuzumab *or rituximab* in combination with idasanutlin, including DLTs, on the basis of the following endpoints:
  - Nature, frequency, severity, and timing of adverse events
  - Changes in vital signs, ECGs, and clinical laboratory results during and following study treatment administration

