### **2.1 SAFETY OBJECTIVES AND ENDPOINTS**

The safety objectives for this study are as follows:

- To determine the recommended Phase II dose (RP2D) for idasanutlin when given in combination with a fixed dose of obinutuzumab *or rituximab* on the basis of the incidence of DLTs during the *DLT windows (see Section 3.1.2.1)* of study treatment
- To evaluate the safety and tolerability of obinutuzumab *or rituximab* in combination with idasanutlin, including DLTs, on the basis of the following endpoints:

Nature, frequency, severity, and timing of adverse events

Changes in vital signs, electrocardiograms (ECGs), and clinical laboratory results during and following study treatment administration

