## 6.3 SAFETY ANALYSES

The major safety objective is to determine the DLT of idasanutlin in combination with obinutuzumab *or rituximab*. Safety will be assessed through summaries of adverse events and changes from baseline laboratory test results, and vital signs. Incidence of clinically significant ECG abnormalities will be reported in patient listings and change from baseline summarized in tables. ECG QT and QTcF intervals will be summarized by descriptive statistics.

All adverse events occurring on or after first study treatment will be summarized by mapped term, appropriate thesaurus levels, and NCI CTCAE, v4.0 grade. All serious adverse events and adverse events of special interest will be summarized and listed.

Deaths reported during the treatment period and during post-treatment follow-up will be listed.

Relevant laboratory and vital sign (temperature, heart rate, respiratory rate, and blood pressure) data will be displayed by time, with Grade 3 and 4 values identified as appropriate.

The primary safety population will include patients who received at least one dose of *any* component of the combination.

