## **7. DATA COLLECTION AND MANAGEMENT**

### **7.1 DATA QUALITY ASSURANCE**

The Sponsor will be responsible for data management of this study, including quality checking of the data. Data entered manually will be collected via EDC through use of eCRFs. Sites will be responsible for data entry into the EDC system. In the event of discrepant data, the Sponsor will request data clarification from the sites, which the sites will resolve electronically in the EDC system.

The Sponsor will produce an EDC Study Specification document that describes the quality checking to be performed on the data. Central laboratory data will be sent directly to the Sponsor, using the Sponsor's standard procedures to handle and process the electronic transfer of these data.

eCRFs and correction documentation will be maintained in the EDC system's audit trail. System backups for data stored by the Sponsor and records retention for the study data will be consistent with the Sponsor's standard procedures.

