## Appendix 1 Schedule of Activities for Patients with Follicular Lymphoma (Dose-Escalation and Expansion) (cont.)

- 
- a The screening period starts with the signing of the Informed Consent Form. Results of standard-of-care tests or examinations performed prior to obtaining informed consent and within the defined window may be used as screening and baseline assessments; such tests do not need to be repeated for screening purposes.
- b Patients who complete maintenance treatment or discontinue maintenance treatment prematurely will undergo assessments at EOM.
- c EOI assessments should be performed 6•8 weeks after Day 1 of the last induction cycle. As an exception, patients who discontinue induction treatment prematurely because of an adverse event may undergo EOI assessments 4•8 weeks after their last dose of study treatment.
- d Patients who complete treatment or discontinue treatment for reasons other than disease progression will undergo assessments every 3 months during the post-treatment FU period, which will continue until disease progression, the start of new anti-lymphoma treatment, or the end of the study, whichever occurs first. The first post-treatment FU visit is 3 months after the EOI visit for patients who do not receive maintenance treatment and 3 months after the last dose for patients who receive maintenance treatment. Patients who experience disease progression will undergo limited assessments every 3 months during the survival FU period, which will continue until the end of the study. The end of the study is defined as the time when all enrolled FL patients have completed or discontinued study treatment and all enrolled DLBCL patients have been followed for at least 1 year after they have completed or discontinued study treatment.
- e Informed consent must be documented before any study-specific screening procedure is performed.

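### Vital-sign change is a safety endpoint with planned summaries and by-time displays, yet no vital-sign value after screening must be entered on the eCRF unless there is an adverse event

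*Combined protocol and SAP*

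**What the plan says.** **Endpoint.** Section 2.1 lists among the safety endpoints "Changes in vital signs, electrocardiograms (ECGs), and clinical laboratory results during and following study treatment administration". The safety objectives in the synopsis say the same.

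**Analysis.** Section 6.3 states: "Safety will be assessed through summaries of adverse events and changes from baseline laboratory test results, and vital signs". It adds: "Relevant laboratory and vital sign (temperature, heart rate, respiratory rate, and blood pressure) data will be displayed by time". On the population it says: "The primary safety population will include patients who received at least one dose of" any component of the combination.

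**Data capture.** Section 4.5.4 has vital signs measured according to the schedules in Appendices 1 and 2, but says that "the associated data, other than the data collected at screening, do not need to be recorded on the eCRF". The one exception, in parentheses, is an adverse event. The notes to both appendices apply a similar rule to assessments shaded in gray.

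**Data route.** Section 7.1: "Data entered manually will be collected via EDC through use of eCRFs". The only direct transfer to the sponsor described there is for central laboratory data.

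**The concern.** An endpoint defined as change needs a baseline value and at least one later value. The plan secures the first for everyone and the second only for patients whose readings are tied to an adverse event. The values that must reach the database are therefore selected by outcome.

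At stake is whether a pre-specified safety endpoint can be reported for the population it is meant to describe. A table of mean change, or a plot over time, built on event-linked readings plus whatever some sites chose to enter would tend to tilt toward abnormal values. A reader of the study report could not tell that from the display.

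**Working it through.** The plan gives no figure to reproduce, so the check sets the passages side by side.

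1. **What the outputs need.** Change from baseline for a patient is the later value minus the baseline value. A display by time needs values at the scheduled times.

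2. **Baseline.** Section 4.5.4 excepts screening values from the non-recording rule. Footnote a of Appendix 1 says that standard-of-care results obtained within the window "may be used as screening and baseline assessments", so screening can serve as baseline. This side is covered for every treated patient.

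3. **Later values.** For a patient with *k* scheduled vital-sign visits after screening and no adverse event, Section 4.5.4 requires entry at none of them: *k* × 0 = 0 required sets, whatever *k* is. The result does not depend on counting visits in the schedules.

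4. **What the exception adds.** Section 5.3.5.6 makes a vital-sign result an adverse event only under stated conditions: it comes with symptoms, changes study treatment, leads to an intervention or a change in concomitant therapy, or is judged clinically significant. An unremarkable reading at a scheduled visit meets none of these. I read the exception in 4.5.4 as covering readings connected with the event, not every reading in a patient who has had one.

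5. **Other routes.** Vital signs are not among the samples sent to a central laboratory (Section 4.5.6.2), and Section 7.1 describes no other transfer of values measured at the site.

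6. **Comparison within the same endpoint.** ECGs stand in the same endpoint bullet, and Section 4.5.7 lists the ECG values to be entered on the eCRF. Vital signs have no such instruction after screening.

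7. **The gray-shading notes.** The shading is lost in the text available for this review, so it cannot be seen whether the vital-signs row is covered. The point does not need it, because 4.5.4 states the rule for vital signs outright.

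Steps 2 to 5 together mean that the required data cannot deliver the endpoint, or the displays in 6.3, for all patients who received at least one dose.

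**The case against.** **The rule is permissive.** Sites may enter values that they need not enter, and the eCRF itself, its completion manual and the EDC specification were not available for this review. This is correct. A reader might infer that no post-screening vital signs will exist in the database, and the documents do not support that. What they show is that none is required without an adverse event. Voluntary entry would give incomplete data with unknown selection.

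**Section 6.3 is loosely worded.** The phrase on changes from baseline could be read as covering laboratory results only, and the by-time display is limited to relevant data, which might mean event-linked readings. This softens the conflict with 6.3. It does not remove the conflict with the synopsis and 2.1, which name change in vital signs directly.

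**Safety signals are still captured.** This stands in full. Section 5.3.5.6 sends clinically significant abnormalities to the adverse-event page, and Section 5.3.5.1 gives signs and symptoms of infusion-related reactions a dedicated eCRF. A reader might infer that patients go unmonitored. They do not: the measurements are still scheduled and made, and only their entry is waived.

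**Which reading stands for a visit.** A reader might also infer that the plan leaves this open, because footnote f of Appendix 1 names a pre-infusion reading for the first cycle and for patients with a reaction, and footnote i of Appendix 2 leaves rituximab monitoring during infusion to the local label. The documents do not support that inference either. A general note in both appendices puts assessments on treatment days before dosing unless otherwise specified. The footnotes add readings during infusion and do not clearly cancel that default.

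**Conclusion.** The contradiction is real and stands in the current text. Change in vital signs is a named safety endpoint, but a patient without an adverse event has zero required post-baseline values. Followed exactly, the plan yields vital-sign displays that rest on event-triggered and voluntary entries and do not represent the safety population.

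The harm is limited to those descriptive displays. DLT decisions and the adverse-event, laboratory, ECG and efficacy analyses do not depend on the rule in 4.5.4. The inconsistency should be corrected, but it does not threaten the trial's main conclusions.

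The conclusion assumes that no other route for vital-sign data exists outside Section 7.1, and that the adverse-event exception applies to event-related readings. How many sets would be entered because of adverse events cannot be derived from the documents.

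**What to change.** Reconcile Section 4.5.4 with the synopsis, 2.1 and 6.3, and adjust the gray-shading notes in Appendices 1 and 2 if they cover the vital-signs row. Either of two routes is enough.

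1. **Keep the endpoint.** Require eCRF entry of one already-scheduled vital-sign set per visit. On treatment days this is the pre-dose set under the existing general note. Leave the monitoring footnotes as they are, exempt routine readings during infusion from entry, and word the endpoint to match what is entered.
2. **Drop the endpoint.** Remove vital-sign change from the synopsis, 2.1 and 6.3, and report vital-sign abnormalities only as adverse events.

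Route 1 costs minor extra data entry. Section 4.5.4 lists five parameters (respiratory rate, pulse rate, temperature, systolic and diastolic pressure). The mark for Cycles 3–6 is misaligned in the available text. If it means one visit per cycle, induction has 3 + 1 + 4 = 8 sets, or 8 × 5 = 40 values per patient. If the Cycle 1 Day 8 and Day 15 marks do not apply to patients on rituximab, they have 6 sets, or 6 × 5 = 30 values. Visits from the end of induction onward come on top.

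Route 2 costs one descriptive endpoint and its displays. Neither route changes treatment or patient monitoring.
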